3.5.1. Schedule of Assessments

Table 1: Schedule of Assessments

Study Period	Screening	Gene Replacement Therapy (In-patient)				Follow-up (Outpatient)					End of Study ^a
		1	2			3	4	5	6	7+	
Visit #		-1	1 ^b	2	3	7	14	21	30	Monthly ^c	18 Months of Age (or ET)
# of Days in Study	-30 to -2	-1	1 ^b	2	3	7	14	21	30	Monthly ^c	18 Months of Age (or ET)
Window						± 2 days					± 7 days (0–14 days at 14 Months of Age)
Informed Consent	X										
Prednisolone Pre-Dosing		X ^q	X	X	X	X	X	X	X ^q		
AVXS-101 Infusion			X								
Bayley Scales/WHO Developmental Milestones ^d (with video) ^e	X								X ^f	X ^f	X
CHOP-INTEND ^g (with video) ^e	X	X ^s				X	X	X	X	X	X
CMAP	X									X ^j	X
Demographic/Medical History	X										
Physical Exam	X		X	X	X	X	X	X	X	X	X
Vital Signs ^h /Weight & Length	X	X	X ⁱ	X	X	X	X	X	X	X	X
12-Lead ECG	X	X	X	X						X ^{j,t}	X
12-Lead Holter Monitoring ^k		X	X	X	X					X ^{j,t}	X
Echocardiogram	X									X ^{j,t}	X
Pulmonary Examination	X	X		X	X	X	X	X	X	X	X
Swallowing Test	X									X ^j	X
Photograph of Infusion Site			X	X	X	X	X	X	X		

Study Period	Screening	Gene Replacement Therapy (In-patient)				Follow-up (Outpatient)					
		1	2			3	4	5	6	7+	End of Study ^a
Visit #	1		2			3	4	5	6	7+	End of Study ^a
# of Days in Study	-30 to -2	-1	1 ^b	2	3	7	14	21	30	Monthly ^c	18 Months of Age (or ET)
Window						± 2 days			± 7 days (0–14 days at 14 Months of Age)	0–14 days	
Hematology/Chemistry/ Urinalysis	X	X ^o		X		X	X	X	X	X	X
CK-MB	X					X			X	X ^r	X
Virus Serology	X										
Capillary Blood Gas		X		X							
ELISA anti-AAV9/SMN Ab	X					X	X	X	X ^l		
Immunology Testing (ELISpot)						X			X ^l		
AAV9 Ab Screen in Mother	X										
Blood for Diagnostic Confirmation Testing	X										
Saliva, Urine, and Stool Samples (for viral shedding) ^p	X			X ^m	X ^m	X	X	X			
Adverse Events ⁿ	X	X	X	X	X	X	X	X	X	X	X
Prior and Concomitant Medications	Collected from 2 weeks before gene replacement therapy until End of Study visit										

Note: Missed visits should be rescheduled as soon as possible, but within 7 days.

Ab = antibody; CHOP-INTEND = Children's Hospital of Philadelphia Infant Test of Neuromuscular Disorders; CMAP = compound motor action potential; ECG = electrocardiogram; ELISA = enzyme-linked immunosorbent assay; ELISpot = Enzyme-linked ImmunoSpot; ET = early termination; WHO = World Health Organization

a The End of Study visit must occur within 0 to 14 days after the date on which the patient reaches 18 months of age (or ET).

b Day 1 assessments will be performed prior to the start of gene replacement therapy infusion.

c The 14 months of age visit must occur within 0 to 14 days after the date on which the patient reaches 14 months of age.

d Developmental milestones will be assessed as defined by Bayley Scale of Infant and Toddler Development, version 3 (independent sitting will be assessed also by WHO Multicentre Growth Reference Study).

e Videos may be submitted for review by a central reader.

f The full Bayley test will be administered every 6 months, starting at Month 6, whereas the Bayley fine and gross motor subtests will be administered at each monthly visit.

g Patients who achieve 3 consecutive CHOP-INTEND scores ≥ 58 will not continue CHOP-INTEND assessments.

h Vital signs include blood pressure, respiratory rate, pulse, axillary temperature, and pulse oximetry

i Vital signs will be continuously monitored throughout the infusion of gene replacement therapy and recorded every 15 minutes for the first 4 hours after the start of infusion, then every hour until 24 hours after the start of infusion. Axillary temperature will be recorded pre- and post-infusion.

j Completed every 6 months, starting at Month 6.

k Serial ECG data will be pulled in triplicate from the Holter monitor at the following time points: pre-dose (within 24h), 2h, 4h, 6h, 8h, 12h, 24h, 36h, and 48h post-dose.

l Additional sampling may be performed at subsequent time points if ELISpot value(s) continue to be elevated, based on further discussion with the Principal Investigator and Medical Monitor.

m Collected at 24 and 48 hours post-dose.

n Serious adverse events are collected from signing of the informed consent through the last study visit. All adverse events that occur from the start of gene replacement therapy through the last study visit are collected.

- o Laboratory samples collected on Day 1 to be processed locally, prior to dosing.
- p Sites participating in the viral shedding sub-study will collect 24-hour full volume samples for urine and feces at 24 and 48 hours. All other sites will collect singular urine and feces samples within 24 hours and 48 hours of dosing.
- q Prednisolone to be given 24 hours prior to scheduled AVXS-101 dosing, and continued as per protocol Section 9.2.1.
- r CK-MB will be collected at Day 60, Month 6, 9, 12, 15, and 18
- s If a Day -1 CHOP-INTEND assessment is not completed, a CHOP-INTEND assessment should be completed on Day 1 prior to dose administration.
- t for patients enrolled in the study prior to amendment 3 and irrespective of study schedule, after signing an updated informed consent form, an echocardiogram, 24-hour Holter monitoring, and 12-lead ECG will be performed at the next scheduled visit and then in accordance with the Schedule of assessments Compound Motor Action Potential Manual

3.6. Patient Selection

The current version of the protocol (v3.0) allows for up to 20 patients, who are 6 months of age or younger at time of gene replacement therapy infusion (Day 1) diagnosed with SMA Type 1 who meet enrollment criteria, which may be either symptomatic or pre-symptomatic and are genetically defined by no functional survival motor neuron 1 gene (*SMN1*) as well as 1 or 2 copies of survival motor neuron 2 gene (*SMN2*). Enrolling up to twenty (20) patients under the broader enrollment criteria is projected to enable enrollment of at least fifteen (15) patients that meet the Intent-to-Treat Population (ITT) criteria. The ITT population is identified as symptomatic patients with bi-allelic *SMN1* deletions and 2 copies of *SMN2* without the *SMN2* gene modifier mutation (c.859G>C) who meet all other study enrollment criteria. In addition, the first three patients enrolled must meet the criteria for the Intent-to-Treat Population to enable a comparison of CHOP-INTEND scores at one-month following gene replacement therapy to enable a comparison of patient response between AVXS-101-CL-303 patients and Cohort 2 patient results from the Phase 1 trial (AVXS-101-CL-101). Patients with 1 copy of *SMN2*, pre-symptomatic patients and patients with the *SMN2* gene modifier mutation (c.859G>C) and other permutations outside of those specified in the ITT population will be evaluated separately as part of additional subgroup analyses. Details of all analyses will be contained within this Statistical Analysis Plan.

3.6.1. Inclusion Criteria

See protocol for details.

3.6.2. Exclusion Criteria

See protocol for details.

3.7. Determination of Sample Size

This study will enroll up to twenty (20) patients with spinal muscular atrophy (SMA) Type 1 who meet enrollment criteria, may be either symptomatic or pre-symptomatic and are genetically defined by no functional survival motor neuron 1 gene (*SMN1*) with 1 or 2 copies of survival motor neuron 2 gene (*SMN2*) and who are < 6 months (< 180 days) of age at the time of gene replacement therapy (Day 1). Enrolling up to twenty (20) patients under the broader enrollment criteria is projected to enable enrollment of at least fifteen (15) patients that meet the Intent-to-Treat Population (ITT) criteria. The ITT population is identified as symptomatic patients with bi-allelic *SMN1* deletions and 2 copies of *SMN2* without the

SMN2 gene modifier mutation (c.859G>C) and will comprise the primary population for evaluation of the primary and secondary endpoints. Study power is based upon efficacy analysis of the ITT population. Furthermore, the first three patients enrolled must meet criteria for the Intent-To-Treat Population to enable a comparison of CHOP-INTEND scores at one-month following gene replacement therapy to enable a comparison of patient response between AVXS-101-CL-303 patients and Cohort 2 patient results from the Phase 1 trial (AVXS-101-CL-101). Patients with 1 copy of *SMN2*, pre-symptomatic patients and patients with the *SMN2* gene modifier mutation (c.859G>C) and other permutations outside of those specified in the ITT population will be evaluated separately as part of additional subgroup analyses.

The two co-primary efficacy endpoints will be assessed in sequence: The endpoint of functional independent sitting will be assessed first and, only if this assessment meets statistical significance will the endpoint of survival be assessed.

The first co-primary efficacy endpoint hypothesis is:

$$H_0: p_{AVXS-101} = 0.1\%$$

versus the alternative

$$H_a: p_{AVXS-101} > 0.1\%,$$

where p is the proportion of functional independent sitting for at least 30 seconds at the 18-month of age study visit.

It is assumed that the true response rate for the primary endpoint is actually zero (or as low as 0.1%) in the population of historical control; the first co-primary efficacy endpoint hypothesis is that the AVXS-101 treated patients achieve a response rate greater than 0.1%. Based upon preliminary results from the ongoing Phase 1 clinical study AVXS-101-CL-101, at least 40% of treated symptomatic patients with bi-allelic deletions of *SMN1* and 2 copies of *SMN2* without the *SMN2* gene modifier mutation (c.859G>C) are expected to achieve the co-primary efficacy endpoint of functional independent sitting for at least 30 seconds at 18 months of age. With the assumption for the true response rate of AVXS-101 for the primary endpoint being in the range of 30% - 40%, a sample size of 15 patients that meet ITT criteria will be enrolled and assuming approximately 30% of patients are excluded from analysis, would yield an ITT population that would provide power of >90% to detect a significant difference with $\alpha=0.025$ using a 1-sided exact test for a binomial proportion.

The second co-primary efficacy endpoint hypothesis:

$$H_0: p_{AVXS-101} = p_{HISTORICAL-FINKEL}$$

versus the alternative

$$H_a: p_{AVXS-101} \neq p_{HISTORICAL-FINKEL},$$

where p is the proportion patients of surviving at 14 months of age.

Based upon preliminary results from the ongoing Phase 1 clinical study AVXS-101-CL-101, at least 80% of treated symptomatic patients with bi-allelic *SMN1* deletions and 2 copies of *SMN2* without the *SMN2* gene modifier mutation (c.859G>C) are expected to achieve the co-primary efficacy endpoint of survival through 14 months of age. It is anticipated that 75% of patients in the PNCR [5] population would not survive beyond 13.6 months of age, and that these control patients will represent a 25% survival rate based upon the natural history of the disease. With this efficacy, an enrolled sample size of 15 patients that meet ITT criteria (assuming 30% of patients are excluded from the analysis) would provide power of >80% to detect a significant difference with $\alpha = 0.05$ using a two sample 2-sided Fisher's exact test, comparing to patient-level data drawn from a published natural history observational study dataset with patients who meet the eligibility criteria for this study (bi-allelic *SMN1* deletions, 2 copies of *SMN2*, age of onset ≤ 6 months of age). The natural history observational study dataset was collected by PNCR network from the study performed at three large, tertiary care centers in the United States (Harvard University, Columbia University, Children's Hospital of Philadelphia; PNCR).

3.8. Treatment Assignment and Blinding

This is an open-label study. All enrolled patients will receive AVXS-101.

3.9. Administration of Study Medication

Refer to [Section 3.5](#) of the SAP.

3.10. Study Procedures and Flowchart

Refer to [Section 3.5](#) of the SAP.

3.11. Statistical Hypotheses

3.11.1. Primary Efficacy Hypothesis

Primary and secondary efficacy analyses will be based on the ITT population, which consists of those symptomatic patients with bi-allelic deletion mutations of *SMN1* and 2 copies of *SMN2* without the *SMN2* gene modifier mutation (c.859G>C). These analyses are to test the superiority of AVXS-101 versus the results from natural observation study (PNCR).

The first co-primary efficacy hypothesis to be tested is:

$$H_0: p_{AVXS-101} = 0.1\%$$

versus the alternative

$$H_a: p_{AVXS-101} > 0.1\%,$$

where p is the proportion of functional independent sitting for at least 30 seconds at the 18-month of age study visit.

The second co-primary efficacy hypothesis to be tested is:

$$\mathbf{H}_0: p_{AVXS-101} = p_{HISTORICAL-FINKEL}$$

versus the alternative

$$\mathbf{H}_a: p_{AVXS-101} \neq p_{HISTORICAL-FINKEL},$$

where p is the proportion surviving event-free to 14 months.

Testing for the first co-primary endpoint, functional independent sitting will first be performed using a 1-sided exact binomial test. Only if the null hypothesis of equality in proportion of functional independent sitting is rejected at $p < 0.025$, will the co-primary endpoint survival improvement be tested using a 2-sided Fisher's exact test on the ITT population, comparing to match patients from the natural observational study (PNCR). This hierarchy approach strongly prevents the Type I error rate from inflation.

3.11.2. Secondary Efficacy Hypotheses

The hypothesis for both co-secondary efficacy endpoints to be tested is:

$$\mathbf{H}_0: p_{AVXS-101} = 0.1\%$$

versus the alternative

$$\mathbf{H}_a: p_{AVXS-101} > 0.1\%,$$

where p is the proportion of patients maintaining the ability to thrive/are independent of ventilatory support.

One-sided exact binomial tests will be executed for secondary efficacy analyses on the ITT population. The same test hierarchy approach will apply to secondary efficacy analyses, which is the co-secondary endpoint of ability to thrive will be tested first. Only if the null hypothesis of ability to thrive is rejected at $p < 0.025$, will the co-secondary endpoint of independent of ventilatory support will be similarly tested. Pre-specification of the order of testing within this hierarchical framework eliminates type 1 error inflation due to multiplicity.

4. ENDPOINTS

4.1. Efficacy Endpoints: (see [Section 8](#) for Details)

4.1.1. Primary Efficacy Endpoints

One co-primary efficacy endpoint is achievement of functional independent sitting. The other co-primary efficacy endpoint is survival, defined as avoidance of either (a) death or (b) permanent ventilation. Permanent ventilation is defined by tracheostomy or requirement of ≥ 16 hours of respiratory assistance per day (via non-invasive ventilatory support) for ≥ 14 consecutive days in the absence of an acute reversible illness, excluding perioperative ventilation. Permanent ventilation, so defined, is considered a surrogate for death.

[figure not shown]
Developmental milestones will be assessed/determined by the qualified Clinical Evaluators at the investigational sites. The assessments will be captured on video from two camera angles. The videos will then be reviewed and verified by an independent, external reviewer for concordance. Only milestones confirmed by the independent reviewer will be utilized for the primary endpoint. Milestones determined by the qualified Clinical Evaluators at the investigational sites will be presented in listings.

4.1.2. Secondary Efficacy Endpoints

One co-secondary outcome will include the proportion of patients who did not require parenteral nutrition prior to therapy who maintain the ability to thrive, defined by all of the following:

- ability to tolerate thin liquids as demonstrated through a formal swallowing test
- no requirement of nutrition through mechanical support (i.e., feeding tube)
- maintenance of weight ($>$ third percentile for age and gender) at 18 months of age.

The other co-secondary secondary outcome will include the proportion of patients who are independent of ventilatory support, defined as requiring no daily ventilator support/usage at 18 months of age, in the absence of acute reversible illness and excluding perioperative ventilation.

4.2.1. CHOP-INTEND Score

There are 16 items in CHOP-INTEND assessment (Section 21.2). A rating of Brazelton behavioral states (Section 21.3) was recorded for each item. As suggested by manual [9], the optimal state for testing is state 4 (“alert, with bright look”) and 5 (“eyes open”). If a subject cannot be tested for an item due to an adverse behavioral state, it should be scored as “CNT” (cannot test) and NOT a zero. In item 1 to 11, 13 and 16, both left and right sides need to be evaluated, and the maximum score should be selected for the best score of the item. If both sides are scored “CNT”, the item should be scored as “CNT”. If only one side scored “CNT”, the other side score should be used for the best score of the item. If any of these 16 items scored “Cannot test” or “CNT”, the total score should be set missing.

4.3. Safety Endpoint

The primary safety endpoint is the development of unacceptable toxicity, defined as the occurrence of any one Grade III or higher, unanticipated, treatment-related toxicity that presents with clinical symptoms and requires medical treatment.

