3.4. Safety Objectives

The safety objectives are to:

- Evaluate the safety of AVXS-101 in patients with SMA Type 1
- Determine the safety of AVXS-101 based on the development of unacceptable toxicity defined as the occurrence of any Common Terminology Criteria for Adverse Events (CTCAE) [CTCAE 04] Grade 3 or higher, unanticipated, treatment-related toxicity.

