4.6.1. Adverse Events

Other than Grade III or higher adverse events used to define unacceptable toxicity in the primary endpoint, all adverse events will be assessed for their seriousness, relatedness to study treatment, relationship to study discontinuation, and severity according to [CTCAE](#) version 4.03 criteria.

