6.2.4.4. Safety Variables

The safety endpoint is defined as the patient meeting the following criteria:

- Unanticipated toxicity event of Grade ≥ 3 (as per CTCAE)
- Adverse events of special interest (see Section 10.3.2.4)
- ‘Possibly Related’ or ‘Probably Related’ or ‘Definitely Related’ to study treatment
- Requires medical treatment or presents with symptoms

This will be collected at all scheduled visits (see [Table 1](#)) from patient’s CRF. Adverse Event collection methods for the observational natural history cohort were not consistent with rigorous Adverse Event collection methods demonstrated in the context of an interventional clinical research study; therefore, only descriptive statistics will be presented.

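### The primary safety endpoint is defined inconsistently: symptoms and treatment in Section 4.3, symptoms or treatment in Section 6.2.4.4, and neither condition in Section 3.4

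*SAP*

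**What the plan says.** Three sections of the SAP describe this endpoint.

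- **Section 3.4 (Safety Objectives)** defines unacceptable toxicity as any CTCAE "Grade 3 or higher, unanticipated, treatment-related toxicity". It sets no condition on symptoms or treatment.
- **Section 4.3 (Safety Endpoint)** uses the same term and gives it its status: "The primary safety endpoint is the development of unacceptable toxicity". It keeps the grade, unanticipated and related conditions and narrows the toxicity to one "treatment-related toxicity that presents with clinical symptoms and requires medical treatment".
- **Section 6.2.4.4 (Safety Variables)** is the only derivation. It opens with "The safety endpoint is defined as the patient meeting the following criteria" and gives four bullets: an "Unanticipated toxicity event of Grade" 3 or above; "Adverse events of special interest (see Section 10.3.2.4"); possibly, probably or definitely related; and "Requires medical treatment or presents with symptoms". No word says whether the bullets are joined by *and* or by *or*.

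Section 4.6.1 refers back to the endpoint as "Other than Grade III or higher adverse events used to define unacceptable toxicity in the primary endpoint", which names only the grade. The adverse event tables in Section 10.3.2 cover Grade 3 and 4, related, serious and special-interest events separately. None counts patients with unacceptable toxicity. Section 13 lists no change to the safety endpoint.

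**The concern.** A programmer who follows Section 4.3 and one who follows Section 6.2.4.4 will flag different patients, and no later section says which is right. This is a conflict within a named endpoint, not detail left to the protocol. The SAP writes the definitions out itself, and Section 2 says it supersedes the protocol's statistical considerations.

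What is at stake is one headline number: how many treated patients met the primary safety endpoint. The study is open-label with all patients treated (Section 3.8). If the conflict stays open, the choice between definitions would be made by people who can already see the events.

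**Working it through.** The SAP attaches no sample size, power or alpha to this endpoint and gives no event rates, so there is no planned figure to reproduce. The check is a comparison of the definitions.

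**Step 1. Common ground.** Sections 3.4, 4.3 and 6.2.4.4 all mention Grade 3 or higher, unanticipated and treatment-related. Take an event that already meets these three conditions.

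**Step 2. What differs.** Let S = symptomatic, T = medically treated, A = in a special-interest category of Section 10.3.2.4. Each is yes or no, so there are 2 × 2 × 2 = 8 types of event. The rules are:

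- 3.4: always counted
- 4.3: S and T
- 6.2.4.4, all bullets required: A and (S or T)
- 6.2.4.4, special-interest bullet not restrictive: S or T

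**Step 3. Enumeration.**

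| S | T | A | 3.4 | 4.3 | 6.2.4.4, all bullets required | 6.2.4.4, A not restrictive |
|---|---|---|---|---|---|---|
| no | no | no | yes | no | no | no |
| no | no | yes | yes | no | no | no |
| no | yes | no | yes | no | no | yes |
| no | yes | yes | yes | no | yes | yes |
| yes | no | no | yes | no | no | yes |
| yes | no | yes | yes | no | yes | yes |
| yes | yes | no | yes | yes | no | yes |
| yes | yes | yes | yes | yes | yes | yes |
| **Types counted** | | | **8** | **2** | **3** | **6** |

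**Step 4. Reading the table.**

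- Only 1 of the 8 types is counted under every column: symptomatic, treated and of special interest.
- Four types are only symptomatic or only treated. Section 3.4 counts all 4 and Section 4.3 counts none. Section 6.2.4.4 counts 2 if all bullets are required and 4 if special interest does not restrict.
- With all bullets required, 6.2.4.4 is neither wider nor narrower than 4.3. One type counts only under 4.3 (symptomatic, treated, not special interest). Two count only under 6.2.4.4 (special interest with just one of symptoms or treatment).
- If special interest does not restrict, 6.2.4.4 contains 4.3 and adds 6 − 2 = 4 types.

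**Step 5. Scale.** Section 3.5 allows up to 20 patients, and safety is assessed on all who are infused (Section 5.1). With 20 treated, one reclassified patient is 1/20 = 5 percentage points; with fewer treated, it is more.

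The totals in the table are counts of event types, not expected numbers of patients.

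**The case against.** The case on the other side has several parts.

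- **Section 3.4 is only an objective**, and an objective may be worded more briefly than its endpoint. That makes it the weaker leg of the conflict. Setting it aside leaves *and* in 4.3 against *or* in 6.2.4.4.
- **The special-interest bullet may not be a requirement.** A reader might infer that 6.2.4.4 drops every related Grade 3 or higher event outside the special-interest categories. The text does not establish that. Where this SAP wants every criterion met, as for ability to thrive in Sections 4.1.2 and 8.2.1, it says all; 6.2.4.4 does not. What can be held against the list is that it is ambiguous.
- **Liver enzyme rises may not be the example they seem.** A reader might take a treated Grade 3 transaminase rise without symptoms as the obvious divergent case. All three sections mention unanticipated toxicity, a word the SAP does not define, and the SAP plainly foresees such rises: steroid tapering tied to ALT and AST (7.4.1), hepatotoxicity as special interest (10.3.2.4) and planned liver analyses (10.4.3, 10.4.4). If such a rise were classed as anticipated, it would fail a condition in Sections 3.4 and 4.3, and in 6.2.4.4 if all bullets are required.
- **Nothing is hidden.** Grade 3 and 4 events, related events by maximum grade, special-interest events and listings are all reported. This is true and limits the harm. Those outputs still do not say which patients met the named endpoint.
- **The endpoint is descriptive.** This is also true, and it removes any effect on error rates.

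**Conclusion.** The inconsistency is real and sits in current text. Sections 4.3 and 6.2.4.4 contradict each other on whether symptoms and treatment are both needed. Section 6.2.4.4 leaves the combination of its bullets and the role of special interest open, and Section 3.4 defines the same term with neither condition. The reported number of patients with unacceptable toxicity is therefore not fixed by the plan.

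The size is 5 percentage points per reclassified patient if 20 are treated. How many patients would be reclassified cannot be stated. A reader might infer that the strictest wording could show none where the broadest shows several, but the SAP gives no event rate to support that. The documents also do not show which section holds the intended definition. The conclusion assumes events that already meet the grade, unanticipated and related conditions. Alpha and power are untouched.

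**What to change.** Before database lock:

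1. Reconcile Sections 3.4, 4.3 and 6.2.4.4 into one definition, worded identically in each.
2. In 6.2.4.4, state explicitly whether the criteria are joined by *and* or by *or*, including the symptom and treatment conditions.
3. Say whether special-interest status is a criterion for the endpoint or only the separate summary of Section 10.3.2.4.
4. Add one table to Section 10.3 with the number and percentage of patients meeting the endpoint. In the same table, show all Grade 3 or higher, unanticipated, related events cross-classified by symptoms (yes/no) and treatment required (yes/no), so that the broader and narrower counts are both visible.

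The cost is some wording, one derivation and one table. The reported rate may turn out less favourable than under the narrowest wording.
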